6.2. Secondary Objectives

To determine the difference in the proportion of COVID-19 patients with clinically meaningful worsening of COVID-19 within 14 days from the start of experimental therapy, as indicated by an increase of at least 2 points on the Ordinal Scale for Clinical Improvement.

To assess the progression of COVID-19 severity during the study as measured by the Ordinal Scale for Clinical Improvement

To assess the progression of COVID-19 severity during the study as measured by the SARS-CoV-2 Symptom Score

To determine SARS-CoV-2 positivity 28 days from the start experimental therapy

To determine mortality rate at 28 days after start of PUL-042 therapy

To assess the requirement for ICU admission within 28 days from the start of experimental therapy

To assess the requirement for mechanical ventilation within 28 days from the start of experimental therapy

To determine the tolerability of PUL-042 Inhalation Solution in this population

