7.14. Early Discontinuation from Dosing and Study Withdrawal

Subjects who have received at least one dose of investigational treatment and are discontinued from dosing should continue to the final assessment at Day 29 according to the schedule of events specified for pre-dose assessments. There will be no post-dose assessments for these subjects.

Should the subject's study participation end prior to the completion of Study Day 15, the following assessments will be conducted as soon as possible after the decision to withdraw from the study is made.

- Serum pregnancy test or urine test (if urine positive, a serum test must be conducted)
- Physical examination
- Vital signs
- Nasopharyngeal or oropharyngeal sample for SARS-CoV-2 testing
- SARS- CoV-2 infection symptom score
- Ordinal Scale for Clinical Improvement assessment
- Adverse event assessment
- Concomitant medication assessment

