2.1.2 Secondary Objectives

- To determine the difference in the proportion of COVID-19 patients with clinically meaningful worsening of COVID-19 within 14 days from the start of experimental therapy, as indicated by an increase of at least 2 points on the Ordinal Scale for Clinical Improvement.
- To assess the progression of COVID-19 severity during the study as measured by the Ordinal Scale for Clinical Improvement
- To assess the progression of COVID-19 severity during the study as measured by the SARS-CoV-2 Symptom Score.
- To determine SARS-CoV-2 positivity 28 days from the start of experimental therapy
- To determine mortality rate at 28 days after the start of PUL-042 therapy
- To assess the requirement for intensive care unit (ICU) admission within 28 days from the start of experimental therapy
- To assess the requirement for mechanical ventilation within 28 days from the start of experimental therapy
- To determine the tolerability of PUL-042 Inhalation Solution in this population

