2.2.2 Secondary Efficacy Endpoints

The secondary efficacy endpoints include the following:

- The difference in the proportion of patients with clinically meaningful worsening of COVID-19 within 14 days from the start of experimental therapy, as indicated by an increase of at least 2 points on the Ordinal Scale for Clinical Improvement.
- Ordinal Scale for Clinical Improvement during the study to determine time course of severity and resolution of disease
- SARS-Cov-2 Symptom Score during the study to determine the time course of disease symptoms and resolution of symptoms
- SARS-Cov-2 test result at Day 29
- All-cause mortality rate through Day 29
- Proportion of subjects requiring ICU admission from Day 1 to Day 29
- Number of ICU Days from Day 1 to Day 29
- Proportion of subjects requiring mechanical ventilation from Day 1 to Day 29
- Number of days on mechanical ventilation from Day 1 to Day 29

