The respiratory symptom score will be calculated by summing the symptom scores from Cough and Shortness of breath or difficulty breathing. The scores from each symptom together with calculated respiratory symptom scores will be summarized by presenting the number and percentage of subjects for each category by visit and treatment group.

The time to the first occurrence of resolution of symptoms defined as the time from the first symptom score of ≥ 1 to a symptom score of 0 will be estimated using the KM method. If a subject had a symptom score of 0 from Baseline through Day 29, then that subject will be excluded from the analysis.

Time to Resolution of Symptoms (days) = (Date of the first symptom score of 0 since the initial score of ≥ 1) - (Date of the initial symptom score of ≥ 1 at or after Baseline) + 1

For each individual symptom and the respiratory symptoms (cough, shortness of breath and difficulty breathing), the KM estimates along with 95% CI, and survival curves will be provided. Based on the KM estimates, the probabilities of experiencing the resolution and associated 95% CIs on Days 15 and 29 will be reported; in addition, the 25%, 50% (median), and 75% percentiles of the time to resolution with associated 95% CIs will be provided, as data permit. The survival rates between treatment groups will be compared using Log-rank test. The p-value from Log-rank test will be presented.

In addition, the time to the first occurrence of improvement of symptoms defined as the time from the initial symptom score of ≥ 1 to a reduction of ≥ 1 point on initial symptom score will also be evaluated for each individual symptom and the respiratory symptoms (cough, shortness of breath and difficulty breathing), using the KM method described above for the analysis of time to resolution of symptoms.

If a subject had a symptom score of 0 from Baseline through Day 29, then that subject will be excluded from the analysis.

Time to Improvement of Symptoms (days) = (Date of the first reduction of ≥ 1 point on initial symptom score of ≥ 1) - (Date of the initial symptom score of ≥ 1 at or after Baseline) + 1

A radar plot will be created by presenting each symptom score at each time point by treatment group.

SARS-CoV-2 Test

The SARS-CoV-2 tests will be performed at the end of the study or early discontinuation visit.

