If the test result for a subject is missing at the end of the study or early discontinuation visit, then the subject will be excluded from the analysis. The proportion of subjects with positive test results within each treatment group will be presented along with a two-sided exact (Clopper-Pearson) 95% CI.

The observed difference in the proportion of subjects with positive test results between treatment groups along with the exact unconditional 95% CI for risk difference will be calculated. The null hypothesis of no difference in proportions of subjects with positive test results between treatment groups will be tested using Fisher's exact method and the p-value will be reported.

Mortality Rate through Day 29

Subject status (Alive/Death) will be recorded in the database. If the vital status of the subject is missing at the end of the study, then the subject will be excluded from the binomial analysis for the mortality rate. The subject will be included in the Kaplan-Meier (KM) analysis with right censoring at the date the subject was last known to be alive.

The mortality rate (proportion of subjects who die) through Day 29 within each treatment group will be analyzed and compared using the method as described in Section 6.1.

If deemed appropriate, an alternative analysis will be performed in which the survival rates will be estimated using the KM method. The KM estimates along with 95% CIs and survival curves will be provided. Based on the KM estimates, the survival probabilities and associated 95% CIs on Days 15 and 29 will be reported; in addition, the 25%, 50% (median), and 75% percentiles of the survival time with associated 95% CIs will be provided, as data permit. The survival rates between treatment groups will be compared using Logrank test and the p-value from Logrank test will be presented.

Subjects requiring ICU admission

Subject data pertaining to ICU admission will be recorded in the database.

The proportion of subjects who are admitted to the ICU from Day 1 to Day 29 within each treatment group will be presented along with a two-sided exact (Clopper-Pearson) 95% confidence interval (CI).

The observed difference in the proportion of subjects requiring ICU admission between treatment groups along with the exact unconditional 95% CI for risk difference will be calculated. The null hypothesis will be tested using Fisher's exact method and the p-value will be reported.

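### The SARS-CoV-2 positivity analysis counts swabs taken at early withdrawal towards a Day 29 endpoint, so the reported proportion need not be Day 29 positivity

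*SAP*

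**What the plan says.** **Objective and endpoint.** SAP 2.1.2 states the objective as "To determine SARS-CoV-2 positivity 28 days from the start of experimental therapy", and Protocol 6.2 has the same objective. SAP 2.2.2 lists the endpoint as "SARS-Cov-2 test result at Day 29".

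**Analysis.** SAP 6.2 says "The SARS-CoV-2 tests will be performed at the end of the study or early discontinuation visit". The missing-data rule opens "If the test result for a subject is missing at the end of the study or early discontinuation visit", and such a subject is left out. The section then forms one proportion positive per arm, one risk difference with an exact interval, and one Fisher test.

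**Timing of the early swab.** Protocol 7.14 sets the timing: "Should the subject's study participation end prior to the completion of Study Day 15, the following assessments will be conducted as soon as possible". The clock starts when the subject decides to leave, and a nasopharyngeal or oropharyngeal sample is on the list. Protocol 11.2 asks every withdrawing subject for the Early Termination assessments and sets no day limit. Subjects who only stop dosing stay on the visit schedule to Day 29 (Protocol 7.8, 7.14 and 11.2). The Day 29 visit has a window of +2 days (Protocol 7.15).

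**Missing data.** SAP 4.4 plans no imputation for this endpoint. The sensitivity analysis specified in SAP 6.3 concerns the primary endpoint only.

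**The concern.** The label and the rule do not match. A subject who leaves in the first week and gives a swab on the way out has a result, so the exclusion rule does not apply and the swab enters the proportion reported for Day 29. Inclusion criterion 1 requires a positive test, so a swab soon after entry mainly reflects when the subject left. It says little about whether the virus had cleared by Day 29.

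Three consequences follow. Early swabs raise the reported proportion in any arm that contributes them, provided they are positive more often than Day 29 swabs. Equal early-swab shares in both arms shrink a true difference. Unequal shares can produce a difference where there is none.

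This is the only one of the nine secondary efficacy endpoints in SAP 2.2.2 that is itself a virus test result, and Protocol section 5 says the data will inform the decision to advance to Phase 3.

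**Working it through.** The documents state no positivity rate, withdrawal rate or power for this endpoint, so there is no plan figure to reproduce. What follows is an illustration.

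**Inputs from the documents.** 50 subjects per arm (SAP 9); two-sided 5% level (SAP 4); Fisher's exact test (SAP 6.2).

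**Assumed inputs.** p29 = positivity at Day 29; pED = positivity at the early-discontinuation swab; w = share of an arm whose only result is an early swab.

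**Formula.** Expected pooled positivity = (1 − w) × p29 + w × pED. Rejection probabilities come from exact enumeration of the two-sided Fisher test at 50 per arm.

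**No true difference (p29 = 20% in both arms, pED = 80%).** For w = 4% (2 of 50): 0.96 × 0.20 + 0.04 × 0.80 = 0.224. For w = 10% (5 of 50): 0.90 × 0.20 + 0.10 × 0.80 = 0.260. For w = 20% (10 of 50): 0.80 × 0.20 + 0.20 × 0.80 = 0.320.

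| Early-swab share, arm A vs B | Pooled positivity | False difference | Fisher rejection |
|---|---|---|---|
| 0% vs 0% | 20.0% vs 20.0% | 0 | 2.8% |
| 10% vs 10% | 26.0% vs 26.0% | 0 | 3.0% |
| 4% vs 10% | 22.4% vs 26.0% | 3.6 points | 4.5% |
| 4% vs 20% | 22.4% vs 32.0% | 9.6 points | 13.9% |

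**Range.** The false difference equals (gap in w) × (pED − p29). Take p29 from 10% to 30% and pED from 60% to 100%, so that pED − p29 runs from 0.30 to 0.90. A 4% vs 10% split then gives 0.06 × 0.30 = 1.8 points to 0.06 × 0.90 = 5.4 points. A 4% vs 20% split gives 0.16 × 0.30 = 4.8 points to 0.16 × 0.90 = 14.4 points.

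**True difference (p29 = 10% vs 30%, pED = 80%, same w in both arms).** The expected difference is (1 − w) × 20 points.

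| w in both arms | Difference | Fisher power |
|---|---|---|
| 0% | 20.0 points | 64% |
| 4% | 19.2 points | 56% |
| 10% | 18.0 points | 46% |
| 20% | 16.0 points | 33% |

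Power falls faster than the difference because the early positives also move both proportions towards 50%.

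**Subjects with no swab.** If m subjects per arm have no result and the observed rates are equal, the extreme fill-ins move the difference by ± m/50: ± 4 points for m = 2, ± 10 for m = 5 and ± 20 for m = 10. A Day-29-only analysis therefore needs its own sensitivity check.

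**The case against.** **Pooling is inferred.** SAP 4.3 summarises data by nominal visit, and the early-discontinuation visit (V6) and Day 29 (V7) are separate columns in the schedule. One could read this as keeping the two swabs apart. But SAP 6.2 is the specific rule: it names the two visits as alternatives and defines one proportion and one test. Pooling is the natural reading, and if it was not intended the text still needs correcting.

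**The exposed group is small.** This stands. Only subjects who leave the study and still attend a visit contribute early swabs. Those who merely stop dosing are followed to Day 29, and those lost to follow-up would normally have no swab. Because Protocol 11.2 sets no day limit, some early-termination swabs may fall close to Day 29.

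**A reader might infer that the comparison is biased.** The documents do not support that. They give no withdrawal rate, and equal early-swab shares with equal positivity leave a null difference at zero. At 4% vs 10% the Fisher rejection rate is still under 5%.

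**A reader might also infer that dropping subjects who die favours the arm with more deaths.** SAP 6.2 does not mention deaths under this endpoint; their exclusion follows only from having no result. The direction depends on whether those who died would have been positive more often than survivors, which the documents do not show. Counting death as not cleared changes the estimand, and deaths are already captured by the mortality and primary endpoints.

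**Existing reporting helps in part.** Disposition by arm (SAP 5.1) and efficacy listings (SAP 6) would show much of who left, and SAP 6.3 allows additional analyses. None of this changes the figure reported for the endpoint.

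**Conclusion.** The mismatch between endpoint and analysis is real. Followed as written, SAP 6.2 reports a mixture of Day 29 swabs and withdrawal swabs, some possibly from the first week, under a Day 29 label. The mixture overstates Day 29 positivity whenever early swabs are positive more often than Day 29 swabs, and it dilutes a true difference even when withdrawal is balanced.

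A false between-arm difference is a risk that depends on unequal early-swab shares. On the assumed rates it is modest at 4% vs 10% and becomes material only with a wide gap such as 4% vs 20%. All sizes rest on assumed positivity and withdrawal figures.

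This is a secondary endpoint, in a study that SAP 4.5 describes as exploratory and leaves without multiplicity adjustment. The effect is on how the virological result is read; the primary result is not touched.

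**What to change.** Revise the SARS-CoV-2 Test paragraphs of SAP 6.2 before unblinding:

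- Main analysis: only the swab from the Day 29 visit (V7, Day 29 +2 days).
- First sensitivity analysis: add the early-discontinuation swabs.
- Second sensitivity analysis: count every subject without a Day 29 swab, including deaths, as positive, or give best-case and worst-case bounds. This is needed because the Day-29-only rule leaves out more subjects, and their withdrawal may itself be informative.
- Report the number without a Day 29 swab, with the reason, by arm.

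The cost is SAP wording, two small extra tables and a slightly smaller denominator in the main analysis. The swabs are already scheduled, so no new data are needed.

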4. GENERAL CONSIDERATIONS FOR DATA ANALYSIS

Unless otherwise specified, continuous variables will be summarized using descriptive statistics

(n, mean, standard deviation, median, minimum, and maximum). Categorical variables will be summarized showing the number and percentage of subjects within each category.

Summary results will be provided for each treatment group. All tabulations will be based on pooled data across centers.

Unscheduled visits will be excluded from the summaries but will be included in the data listings.

All statistical tests will be two-sided and tested at the 5% level of significance.

Analyses will be performed using SAS for Windows statistical software, version 9.4 or higher (SAS, Cary, NC), except where other software may be deemed more appropriate.

CTI will perform all efficacy and safety analyses described in this SAP.

Subject data will be listed, sorted by treatment group and subject number. When applicable, listings will be additionally sorted by visit and assessment date/time.

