6. EFFICACY ANALYSES

All efficacy analyses will be carried out using the ITT set. Data on all efficacy endpoints will be listed and tabulated as appropriate.

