Subjects who have died without ICU admission during the study will be counted as requiring ICU admission for the analysis.

Number of ICU Days

The number of ICU days from Day 1 to Day 29 will be calculated based on the ICU admission and discharge dates recorded in the eCRF. The calculated number of ICU days will be compared between treatment groups using 2-sided Student's t-test. The 95% CI and p-value will be presented.

If the Student's t-test normality assumption is found to be clearly violated, a sensitivity analysis will be performed using a non-parametric Wilcoxon rank-sum test. The p-value from the test will be presented.

Subjects who died will be assigned as hospitalized in the ICU for the number of days remaining from the day of death to Day 29 for the analysis. Subjects who are alive and never admitted into the ICU will be included in the analysis with a value of zero ICU days.

Subjects who were at ICU at study completion will be assigned an ICU end date equal to the date of completion for the purpose of deriving number of ICU days.

Subjects requiring mechanical ventilation

Subject data pertaining to mechanical ventilation use will be recorded in the database.

The proportion of subjects who were on mechanical ventilation from Day 1 to Day 29 within each treatment group will be analyzed and compared using the method described above for the analysis of subjects requiring ICU admission.

Subjects who have died without mechanical ventilation during the study will be counted as requiring mechanical ventilation for the analysis.

Number of days on mechanical ventilation

The number of days on mechanical ventilation from Day 1 through Day 29 will be calculated based on the start/stop dates of mechanical ventilation recorded in the eCRF. Number of days on mechanical ventilation will be compared between treatment groups using 2-sided Student's t-test. The 95% CI and p-value will be presented.

If the Student's t-test normality assumption is found to be clearly violated, a sensitivity analysis will be performed using a non-parametric Wilcoxon rank-sum test. The p-value from the test will be presented.

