9. SAMPLE SIZE AND POWER CALCULATIONS

The trial size of 100 subjects (50 PUL-042 inhalation solution: 50 placebo) was chosen based on clinical considerations. The rates of infection to adequately estimate a sample size for a statistically significant result are unknown.

Enrolled subjects will be randomized with equal probability to receive blinded treatment consisting of either PUL-042 or placebo.

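### The binomial mortality analysis drops subjects of unknown vital status but counts every recorded death, the Kaplan-Meier analysis that would use their follow-up is optional, and no rule covers lost subjects in the ICU and ventilation proportions

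*SAP*

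**What the plan says.** **Mortality (SAP 6.2, Mortality Rate through Day 29).** Deaths through Day 29 are compared by the methods of SAP 6.1: Clopper-Pearson intervals by arm, an exact unconditional interval for the difference, and Fisher's test. When vital status is missing at study end, "then the subject will be excluded from the binomial analysis for the mortality rate". The next sentence treats the same person differently: "The subject will be included in the Kaplan-Meier (KM) analysis with right censoring at the date the subject was last known to be alive". That second analysis is conditional: "If deemed appropriate, an alternative analysis will be performed in which the survival rates will be estimated using the KM method". No criterion or decision-maker is named. The Kaplan-Meier analyses of clinical improvement and of symptom resolution, in the same section, carry no such condition. SAP 4.4, Table 1, already gives a censoring rule for survival.

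**ICU and ventilation (SAP 6.2).** The ICU endpoint is "The proportion of subjects who are admitted to the ICU from Day 1 to Day 29 within each treatment group", and "Subjects who have died without ICU admission during the study will be counted as requiring ICU admission for the analysis". Ventilation is handled in the same way. Neither has a rule for subjects lost to follow-up.

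**General rules.** SAP 6: "All efficacy analyses will be carried out using the ITT set". SAP 4.4: apart from a short list of exceptions, which does not include ICU or ventilation status, missing data are left missing and nothing is imputed. SAP 4: "All statistical tests will be two-sided and tested at the 5% level of significance".

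**The concern.** Whether a subject enters the mortality denominator depends on the outcome. A death on Day 20 counts. Survival to Day 20 followed by loss does not, although those 20 days of known survival are information. If one arm loses more subjects after follow-up has begun, its estimated mortality rises with no true difference between arms.

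The ICU and ventilation proportions include death, so a subject of unknown vital status with no recorded admission has unknown status there too. The SAP settles this for mortality and for the SARS-CoV-2 test but not for these two endpoints. Two programmers could follow the text in good faith and use different denominators.

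The SAP plans no missing-data sensitivity analysis (6.3), and subjects who withdraw after dosing starts are not replaced (protocol 11.2). Protocol section 5 says the data will inform the feasibility of Phase 3 and possible emergency authorisation. With few deaths, the estimates themselves will be read closely.

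**Working it through.** **Inputs from the documents.** 50 per arm: "The trial size of 100 subjects (50 PUL-042 inhalation solution: 50 placebo) was chosen based on clinical considerations". Control mortality of 5% is the planning value in the stopping rule (SAP 8).

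**Assumptions.** No loss rate is given. I take 20% v 5% as the main case, with 10% v 5% and 20% v 0% alongside. A 15% risk is added as a higher value.

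**The plan's own figures.** The only recomputable ones are the stopping probabilities. With SE = √[0.05×0.95/25 + p(1−p)/25], the chance that the difference exceeds 0.075 is 90.1%, 61.7% and 11.2% for p = 25%, 15% and 5%. The SAP states 90%, 62% and 11%, so they reproduce. The point made here does not rest on them.

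**Exclusion rule.** Let p be the true risk, equal in both arms, d the loss proportion unrelated to prognosis, and q the chance that an event precedes the loss in a subject who would have both. Recorded events are e = p(1−d) + p·d·q. Known event-free subjects are (1−p)(1−d). The expected estimate is e / [e + (1−p)(1−d)].

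At p = 5% with loss spread evenly (q = 0.5):
- d = 20%: e = 0.040 + 0.005 = 0.045; 0.045 / (0.045 + 0.760) = 5.59%
- d = 5%: e = 0.0475 + 0.00125 = 0.04875; 0.04875 / (0.04875 + 0.9025) = 5.12%
- difference: +0.47 points

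Spurious difference (arm with more loss minus the other), in points:

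| True risk | Loss | Early loss (q=0) | Even (q=0.5) | Late loss (q=1) |
|---|---|---|---|---|
| 5% | 10% v 5% | 0.00 | +0.14 | +0.28 |
| 5% | 20% v 5% | 0.00 | +0.47 | +0.92 |
| 5% | 20% v 0% | 0.00 | +0.59 | +1.17 |
| 15% | 20% v 5% | 0.00 | +1.23 | +2.41 |

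Under these assumptions (equal risk, loss unrelated to prognosis), Kaplan-Meier targets a difference of zero in every cell. With no loss it equals the simple proportion.

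**Test size.** In 60,000 simulated trials with even 20% v 5% loss and no true difference, Fisher's test on the exclusion rule rejected in 2.2% at p = 5% (0.7% with no loss) and 3.7% at p = 15% (2.3% with no loss). Both stay under 5%.

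**A hypothetical trial.** Three recorded deaths per arm, 10 v 2 subjects lost:
- exclusion rule: 3/40 = 7.5% v 3/48 = 6.25%, Fisher p = 1.0
- lost subjects kept as alive: 3/50 = 6% v 6%
- all lost subjects counted as dead: 13/50 = 26% v 5/50 = 10%

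**ICU and ventilation: two readings.** The ITT denominator, with no admission recorded, suggests counting a lost subject as event-free. The expected estimate is then e. At 5% risk and even 20% v 5% loss this is 4.5% v 4.875%, or −0.375 points; at 15% it is 13.5% v 14.625%, or −1.125 points. SAP 4.4 suggests treating the status as missing and excluding the subject. The exclusion formula then applies, giving +0.47 and +1.23 points. The zero-day rules in SAP 6.2 do not decide the matter: they concern day counts only and do not say who is alive when vital status is missing.

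**The case against.** **The bias is small and may not arise.** At 20% v 5% even loss, 0.47 points is about a quarter of one subject in 50. It vanishes if loss is early, and it depends on loss rates that the documents do not give. These are secondary endpoints in a study the SAP calls exploratory, without multiplicity adjustment. All of that stands and limits the weight of the point.

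**Kaplan-Meier is not a full cure.** It assumes that loss is unrelated to prognosis. Suppose retained subjects have 5% risk, lost subjects have 30% unseen risk, and 10 v 2 are lost before any event. True rates are (2+3)/50 = 10% and (2.4+0.6)/50 = 6%. Exclusion gives 5% v 5%, and Kaplan-Meier would give the same. This stands.

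**Replacing the exact methods would be a poor trade.** At 5% mortality, 50 × 0.05 = 2.5 deaths per arm are expected, and the chance that at least one arm has none is 1 − (1 − 0.95^50)² ≈ 15%. Greenwood variance is then zero in that arm. This stands, and it is why the exact analysis is kept.

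**Stronger readings that a reader might infer.**
- *That the ICU and ventilation analyses keep lost subjects as event-free, so that the same missing people bias mortality and these endpoints in opposite directions.* The SAP states no such rule, and 4.4 points the other way. Even on the event-free reading, opposite signs need loss unrelated to prognosis and spread over follow-up: the exclusion bias is zero for early loss and the event-free bias is zero for late loss. In the informative example above, event-free counting gives 4.0% v 4.8%, so both rules hide a true excess in the arm with more loss.
- *That FEV1 falls on PUL-042 make unequal loss likely.* Those falls can end dosing, but protocol 7.8, 7.14 and 11.2 require subjects who stop dosing to be followed to Day 29. The link to missing vital status is weak.
- *That every death is counted.* Only recorded deaths are; those after loss are unseen.

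**Conclusion.** The point holds for mortality. The binomial rule makes exclusion depend on outcome and overstates mortality in the arm with more loss during follow-up, while the analysis that uses the partial follow-up is discretionary and could be chosen after the data are seen. The expected bias is under 1 point at 5% mortality with 20% v 5% loss, assuming equal true risk and loss unrelated to prognosis, and Fisher's test does not exceed its nominal level.

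For ICU-or-death and ventilation-or-death, the finding is a gap: handling of lost subjects is unstated, two readings are defensible, and the direction of any bias is undetermined. The documents do not support a claim of opposing biases or an expectation of unequal loss. The change is worth making because it is cheap and removes a choice that is now open, rather than because a large error is expected.

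**What to change.** In SAP 6.2:
1. Delete the condition that opens the Kaplan-Meier sentence under mortality. Always report the Day 29 Kaplan-Meier mortality estimate by arm, with the difference and its confidence interval, beside the exact binomial and Fisher analysis.
2. Apply the same rule to ICU-or-death and ventilation-or-death: time to first event, censored at last contact, reported beside the exact proportions. State explicitly how lost subjects enter those proportions.

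**Cost.** SAP wording and minor programming. The survival censoring rule is already in SAP 4.4, and SAP 6.2 already relies on recorded ICU admission dates and ventilation start dates. The downside is that Kaplan-Meier intervals are approximate with few events and Greenwood variance is zero in an arm with no deaths, so the exact analysis must stay. The added analysis does not protect against loss that is related to prognosis.

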Subjects who died will be assigned as being on mechanical ventilation for the number of days remaining to Day 29 for the analysis. Subjects who had mechanical ventilation ongoing at study completion will be assigned a mechanical ventilation end date equal to the date of completion for the purpose of deriving duration of mechanical ventilation. Subjects who are alive and never placed on mechanical ventilation will be included in the analysis with a value of zero days on mechanical ventilation.

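### ICU days and ventilator days: a late death can score better than a survivor's longer stay, and the main test is a t-test on counts with a built-in spike at zero

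*SAP*

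**What the plan says.** SAP 6.2 sets parallel rules for the two day counts.

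- **Main test.** "The calculated number of ICU days will be compared between treatment groups using 2-sided Student's t-test", and "Number of days on mechanical ventilation will be compared between treatment groups using 2-sided Student's t-test". Each comes with a 95% CI and a p-value.
- **Role of Wilcoxon.** For both endpoints, if the t-test's "normality assumption is found to be clearly violated, a sensitivity analysis will be performed using a non-parametric Wilcoxon rank-sum test". No criterion, time point or decision-maker is named. SAP 6.3 adds that further analyses do not replace the planned ones.
- **Zeros.** "Subjects who are alive and never admitted into the ICU will be included in the analysis with a value of zero ICU days". Likewise, "Subjects who are alive and never placed on mechanical ventilation will be included in the analysis with a value of zero days on mechanical ventilation".
- **Deaths.** "Subjects who died will be assigned as hospitalized in the ICU for the number of days remaining from the day of death to Day 29". The ventilation counterpart reads: "Subjects who died will be assigned as being on mechanical ventilation for the number of days remaining to Day 29 for the analysis".

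The surrounding text also matters. Entry requires an ordinal score of 4 or less (Protocol 7.2.1), and subjects who need high-flow oxygen or ventilation are excluded (Protocol 7.2.2). The proportions admitted and ventilated are separate endpoints tested with Fisher's exact test, and deaths without admission or ventilation count as events there (SAP 6.2). SAP 4.5 calls the study exploratory and makes no multiplicity adjustment. Neither document gives an ICU rate, a ventilation rate, a standard deviation or a power for the day counts.

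**The concern.** There are two linked problems.

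The first is the scoring of death. The days-remaining rule is presumably meant to stop death from looking like a short stay. It does so only for early deaths. The later the death, the smaller the number added, so a subject who dies near the end of follow-up can look better than one who recovered after a longer stay. This follows from the text and needs no assumption about rates.

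The second is the choice of test. Nobody enters on high-flow oxygen or ventilation, and living subjects without admission or ventilation are set to zero. A spike at zero with a right tail is therefore built in. Whether normality is clearly violated is in effect settled before any data are seen, yet the plan treats it as an open question and keeps the t-test as the main result whatever the answer. At stake are the headline p-value and interval for two secondary endpoints, which would rest on a few large values.

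**Working it through.** **1. Death rule (from the text).** For a death on Day d, the days remaining are 29 − d, or 29 − d + 1 if the inclusive duration rule in SAP 4.6 applies. SAP 6.2 does not say which.

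- Death on Day 27, never admitted: 29 − 27 = 2, or 3. A survivor with a 10-day stay scores 10.
- Death on Day 29, never admitted: 0 or 1. On the first count this equals a survivor who was never admitted, although the ICU proportion counts the same subject as an event.
- Death in the ICU on Day 27 after admission on Day 20, if days already accrued are kept: Day 20 to Day 29 gives 29 − 20 + 1 = 10. That ties with the 10-day survivor and is lower than any survivor's longer stay.
- Death on Day 5: 24 or 25. Early deaths are scored badly, as intended.

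**2. Simulation inputs.** From the documents: 50 per arm, two-sided 5%. There is no stated figure to reproduce. Assumed: ICU share 2% to 50%; admission on Days 2 to 12; stay of 1 day plus a rounded exponential with mean 10, cut at Day 29; 30% of admitted subjects carried to Day 29 as deaths; no deaths without admission. There were 20,000 trials for the t-test and Fisher, and 8,000 for the tie-corrected Wilcoxon.

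**3. Shape.** A normal curve with the same mean and SD puts a share Φ(−mean/SD) below zero days.

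- 5% share: Φ(−0.68/3.54) = Φ(−0.19) = 42%; skewness 5.7.
- 30% share: Φ(−4.13/7.89) = Φ(−0.52) = 30%; skewness 1.8.

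Shapiro-Wilk rejected normality in every simulated arm examined, even at a 50% share (all-zero arms were counted as rejections).

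**4. Undefined case.** With no admissions and no deaths, all 100 values are zero and the t statistic does not exist. At a 2% share the chance is 0.98^100 = 13%, and the simulation also gave 13%.

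**5. Type I error.**

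| ICU share, both arms | t-test | Wilcoxon |
|---|---|---|
| 2% | 0.3% | 1.5% |
| 5% | 2.5% | 4.8% |
| 10% | 4.6% | 4.8% |
| 15% to 50% | 4.9% to 5.1% | 4.6% to 5.0% |

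The simulation error of the t-test figures near 5% is √(0.05 × 0.95/20,000) = 0.15 points, so 5.1% is consistent with the nominal level.

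**6. Power when the arms differ in admissions.**

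| ICU share, by arm | t-test | Wilcoxon | Gap (points) | Fisher, any ICU |
|---|---|---|---|---|
| 5% vs 15% | 29% | 38% | 9 | 24% |
| 5% vs 20% | 50% | 64% | 14 | 51% |
| 10% vs 25% | 38% | 51% | 13 | 41% |
| 10% vs 30% | 56% | 71% | 15 | 63% |
| 20% vs 40% | 42% | 57% | 15 | 51% |

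An alternative stay model (zero-inflated gamma, shape 1.5, mean stay about 10 to 11 days) gives 50% vs 64% at 5%/20% and 55% vs 72% at 10%/30%. Across both models the gap is about 9 to 17 points.

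**7. Power when only length of stay differs.** Under the gamma model, with equal admission and mean parameters of 5 and 12 days:

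- 20% admitted in both arms: t-test 21%, Wilcoxon 5%.
- 30% admitted in both arms: t-test 36%, Wilcoxon 7%.

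**The case against.** The best defence has four parts.

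- **Validity.** A two-sample t-test does not need normal raw data at 50 per arm, and a difference in mean days is an interpretable estimate that a Wilcoxon p-value does not supply. This stands. A reader might infer that the t-test produces false positives; the type I errors above do not support that.
- **Duplication.** With mostly zeros, Wilcoxon is close to a test of any versus none. At 5% vs 20% its log p-value correlated 0.997 with that of a chi-square on ICU yes/no, and the two agreed on significance in 97% of trials. The SAP already tests that proportion with Fisher's exact test. Length of stay is what a day count adds, and Wilcoxon can miss it almost entirely (step 7). This stands, and it is why the mean difference must stay beside the rank test.
- **Data dependence.** A reader might infer that the plan picks its main test after seeing the data. It does not: the t-test stays the main result either way, and if normality is sure to fail then Wilcoxon will be reported anyway. What remains is a condition with no criterion and no real function.
- **Death scoring.** A reader might infer that death always beats recovery, or that everyone never admitted scores zero. Neither is so: early deaths score high, and the zero rule covers only living subjects. Mortality is also tested separately, and a change of test alone does not cure the scoring. Even so, none of this removes the late-death reversal within these two endpoints.

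**Conclusion.** The point holds in a limited form. The death rule is faulty on the text alone: a late death can score better than a survivor's longer stay on both endpoints.

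The choice of test is partly a trade-off. The t-test is conservative when ICU use is rare, near nominal otherwise, and undefined if every value is zero. It is about 9 to 17 points less powerful than Wilcoxon when the arms differ in admissions, and clearly more powerful when only length of stay differs. The documents do not say which pattern to expect, so it would be wrong to conclude that Wilcoxon is better throughout. The normality condition serves no purpose, because its answer is in effect known.

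The power and error figures rest on assumed ICU shares and stay lengths and were run for ICU use. For ventilator days the scoring argument carries over directly; the figures carry over only so far as ventilation rates and durations are similar. Severity is limited: these are two secondary endpoints in an exploratory trial, and the primary analysis is not affected.

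**What to change.** In SAP 6.2, for both endpoints:

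1. Rank any death up to Day 29 worse than every survivor, whatever the day or place of death.
2. Report the Wilcoxon rank-sum test unconditionally, tie-corrected or exact.
3. Delete the sentence beginning "If the Student's t-test normality assumption is found to be clearly violated, a sensitivity analysis will be performed" and its counterpart for ventilator days.
4. Keep the mean difference in days beside it, with a permutation p-value or bootstrap CI in place of the t-test. State which number of days a death contributes to that mean, since a mean cannot use a rank, and print the number of deaths per arm next to it.
5. State that no test is run if all values are zero.

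The cost is SAP wording before unblinding. The dates and vital status needed are already to be recorded, and the protocol's statistical section names no test for these counts. The downside is that the rank test largely repeats the Fisher result and has almost no power for an effect on length of stay alone. Item 4 is there to cover that.
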